Predictor and Outcome variables: Screening test acceptance by miners is measured for each eligible work shift and cumulative acceptance rate (i.e., outcome) is calculated over the study timeframe (frequency of tests /number of eligible shifts worked, max=less than 60). Characteristics predicting acceptance include self-reported educational and racial/ethnic minority status (from baseline questionnaire), self-reported prior SARS-CoV-2 infection or vaccination (from app), evidence of prior infection (from a prior positive screening test), and daily county incidence and prevalence infection rates (from publicly available data). Focus group discussions and/or individual interviews will be performed in a sample of subjects at the intervention mine (in NM) to better understand ‘testing hesitancy’ towards the end of the study, using an interview script and trained interviewers. Only approved study members will be performing interviews.

Expected outcomes: We anticipate a higher testing acceptance rate among non-Hispanic whites and those with higher self-reported educational status. Conversely, we expect lower acceptance rates among those with prior infection (or vaccination), and during time

PROTOCOL TITLE: Keeping rural minority ‘essential’ workplaces open safely during the COVID-19 pandemic: The role of frequent point-of-care molecular workplace surveillance for miners

intervals in which incidence of infection in the County is either trending down or at a low level.

7.2. Specific Aim 2:

Predictor and Outcome variables: Predictor variable is the sensitivity of the screening test in our study conditions. Outcomes are a) the sensitivity of the screening test reported by others in controlled settings, and b) viral load measurements in upper respiratory specimens (i.e., repeat nasal and NP swab).

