Expected outcomes: We anticipate that as compared to the control mine, the intervention mine demonstrates lower incident seropositivity, and that workplace surveillance is cost-effective **over twelve months**.

7.4. Specific Aim 4:

Predictor, and outcome variables: The outcome variable for hypothesis 4A of incident seropositivity, is defined as in Aim 3. Predictor variables include frequency of cloth face-covering use outside the mine, occupational dust exposure intensity, presence of lung

PROTOCOL TITLE: Keeping rural minority ‘essential’ workplaces open safely during the COVID-19 pandemic: The role of frequent point-of-care molecular workplace surveillance for miners

disease (historically or measured by sputum inflammation), and race/ethnicity status. Additional predictor variables for hypothesis 4B are specific barriers and facilitators. Additional outcomes for hypothesis 4B are test and vaccine uptake.

Expected outcomes: We anticipate that low levels of use of cloth face-coverings in public settings outside the mine, high levels of occupational dust exposure intensity, baseline dust-related lung disease, and racial/ethnic minorities are each associated with a greater relative risk for incident seropositivity than those without these characteristics. We anticipate that additional predictor variables, as outlined in the previous paragraph, affect test and vaccine uptake.

8. Research Setting

Recruitment, enrollment, and data collection will be conducted at the Peabody El Segundo mine in McKinley County, NM (i.e., intervention mine) and the Peabody Caballo and Rawhide mines at Campbell County, WY (i.e., control mine). Both surface coal mines, operated by the same company, have similar engineering, administrative and personal protective measures in place, including SARS-CoV-2 symptom & fever screening.

Baseline survey will be collected from both intervention and control mine sites but the additional questionnaire (and sputum collection) will be limited to the NM mine site only.

Confirmatory diagnostic tests, which are standard of care RT-PCR tests, will be conducted at TriCore Reference Laboratories from samples collected at the Peabody El Segundo mine or at the Cibola General Hospital (where TriCore Reference Laboratories currently provide reference laboratory services). The results from the standard of care test will be provided by TriCore to the study investigators. This does not require a data user agreement.

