Additional questionnaire: Demographics (age or DOB, gender or sex, race and ethnicity, education, household income, insurance, Mailing residential address and if PO Box, physical mailing address, phone number, medical history, smoking, history of prior COVID hospitalization, Testing and vaccination history	Once between 6 and 12 months, using paper, or electronic (e.g. REDCap)	None

PROTOCOL TITLE: Keeping rural minority ‘essential’ workplaces open safely during the COVID-19 pandemic: The role of frequent point-of-care molecular workplace surveillance for miners

Web-based phone app questionnaire: Symptoms; frequency of cloth face-covering use outside the mine ; vaccination history, infected contacts, & history of prior COVID infection	Each work shift via the phone app	
Measured fever screen	Each work shift measure, recorded via REDCap (normal vs. abnormal)	
Nasal swab (self-collected) screening test	Alternate shift collection plus test acceptance data entered into REDCap	None
Nasopharyngeal swab (trained professional or TP-collected) diagnostic test (RT-PCR, TriCore labs)	All abnormal screening tests (collected at TriCore Cibola) & sample (n=approximately 200) of normal screening tests (collected at mine site) plus test acceptance data entered into REDCap	None prescribed
Nasal (self-collected) and nasopharyngeal swab (TP-collected) research test (RT-qPCR, [name] labs)	All abnormal & sample of normal tests as above	None prescribed
Serology	Blood sample at baseline, 3, 6, and approximately 12 months plus test acceptance data entered into REDCap	
Occupational dust exposure intensity	Every work shift via job-exposure matrix created by occupational safety team via REDCap	
Daily county incidence and prevalence data	Recorded daily by study coordinator from public health records entered into REDCap	
Focus group discussions and/or individual interviews to study “testing hesitancy”	Yes	No
Spontaneous home collected sputum sample	Yes once at approximately 12 months	No

12.1. Specific Aim 1:

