Power calculation: Based on representative seroprevalence/molecular prevalence rates for similar communities (36), we anticipate a 10% baseline seropositivity with incident seropositivity at 6 months at 5% for the intervention mine and a baseline seropositivity of 5% in the control mine. We anticipate similar power calculations to apply up to 12 months. We explored a range of control miner incident seroprevalence values that would have 80% power when comparing frequencies at the two mines using chi-square tests. We expect 80% power if incident seropositivity at the control mine is $\geq 9\%$ ($\alpha=0.025$).

13.4. Specific Aim 4:

Statistical analysis: Chi-square and logistic regression analyses will be used to explore how miner characteristics are associated with baseline seropositivity. Generalized linear models for repeated binary outcomes will be used to assess how predictor variables (noted in Table 7) and covariates (as noted in Aim 3) are associated with incident seropositivity at 3, 6, & approximately 12 months. Both analysis strategies will include mine type as a covariate and will add predictor and outcome variables noted in Table 7.

Table 7: List of predictor and outcome variables for Aim 4

Predictor and outcome variables	Time of measurement	Procedure for ascertainment
Frequency of cloth face-covering use outside the mine	On the day of the screening test; Mean summary variable over the one week before the test	Self-report, via the app, every work shift
Occupational dust exposure intensity	On the day of the screening test; Mean summary variable over the one week before the test	Mine safety team, via job-exposure matrix, every shift
Presence of lung disease	Baseline	Baseline survey
Race/ethnicity status	Baseline (at study enrollment)	Self-report via questionnaire
Facilitators and barriers	Between 6 and 12 months	Self-report via questionnaire
Test and vaccine uptake	Between 6 and 12 months	Self-report via questionnaire

Power calculation: We assessed power, using simulation for incident seropositivity at 6 months with mine type as covariate and a predictor miner variable, such as high dust exposure. We anticipate similar power calculations up to 12 months. We assumed the miner variable, present in 1/3 sample, will increase the probability of incident seropositivity by 0.10. For a logistic regression analysis and this setup, power is $>96\%$.

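### Section 13.4 adds to the exploratory baseline-seropositivity model four Table 7 variables that have no baseline measurement, two of them collected only at the NM mine

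*Combined protocol and SAP*

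**What the plan says.** Section 13.4 begins with the baseline analysis: "Chi-square and logistic regression analyses will be used to explore how miner characteristics are associated with baseline seropositivity". Its second strategy is a set of generalized linear models for incident seropositivity at 3, 6 and about 12 months, using the Table 7 predictors and the Aim 3 covariates. A closing sentence then governs both: "Both analysis strategies will include mine type as a covariate and will add predictor and outcome variables noted in Table 7". Nothing limits the baseline model to the Table 7 rows that are known at enrolment.

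Table 7 has six rows. Lung disease and race/ethnicity are baseline items. Face-covering use and dust intensity are recorded every shift and timed as "On the day of the screening test; Mean summary variable over the one week before the test". Facilitators/barriers and test/vaccine uptake are timed "Between 6 and 12 months". Section 8 says that "the additional questionnaire (and sputum collection) will be limited to the NM mine site only", and the overview table in section 12 shows no such questionnaire at the control mine. Section 7.4 names test and vaccine uptake as outcomes of hypothesis 4B.

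**The concern.** A model of baseline seropositivity describes a state that is fixed at enrolment. Predictors recorded later may have been changed by that state: a miner who has been infected may mask differently, or be more or less ready to be tested or vaccinated. A coefficient for such a variable cannot be read as a risk factor for having been infected. Adjusting for it can also distort the coefficients of the proper baseline predictors, race/ethnicity and lung disease.

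The closing sentence also conflicts with itself. It requires mine type in the model and adds variables that exist at only one mine. Whoever runs the analysis must decide, without guidance from the plan, which variables or which miners to drop.

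**Working it through.** The plan gives no figure for the baseline model. Its only Aim 4 power statement concerns incident seropositivity, so there is nothing of its own to reproduce here.

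**Step 1: timing and coverage** (Table 7; section 8; section 12 overview table; section 23 for the app message sent to WY).

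| Table 7 variable | When recorded | Mines | Known at enrolment? |
|---|---|---|---|
| Face-covering use | each shift, by app | no control-mine exclusion | no |
| Dust intensity | each shift, job-exposure matrix | no control-mine exclusion | no |
| Lung disease | baseline survey | both | yes |
| Race/ethnicity | enrolment | both | yes |
| Facilitators/barriers | once, 6 to 12 months | NM only | no |
| Test and vaccine uptake | once, 6 to 12 months | NM only | no |

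Two of six are baseline variables, four of six have no baseline measurement, and two of six are NM-only.

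**Step 2: miners lost.** The ceilings in section 5 are fewer than 250 (NM) and fewer than 350 (WY), so at most 249 + 349 = 598. If an NM-only item enters a complete-case fit, every WY miner drops out: 349/598 = 58%. With the baseline rates assumed in section 13.3 (10% NM, 5% WY), expected baseline positives are 0.10 × 249 = 24.9 and 0.05 × 349 = 17.5, or 42.4 in all. The share lost is 17.5/42.4 = 41%.

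**Step 3: mine type.** Among the remaining NM miners, mine type is constant and duplicates the intercept. A design matrix with intercept, mine type and one NM-only variable has three columns and rank 2, so the mine-type coefficient cannot be estimated. This step needs no causal assumption.

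**Step 4: what a later variable can show.** The uptake figures here are assumed, since the documents give none. Let u0 and u1 be later uptake in baseline-seronegative and baseline-seropositive miners. The odds ratio is symmetric, so the uptake odds ratio in an unadjusted baseline model is [u1/(1 − u1)] / [u0/(1 − u0)].

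- u0 = 60%, u1 = 60%, 50%, 40%, 30%: odds ratio 1.00, 0.67, 0.44, 0.29.
- u0 = 80%, u1 = 60%: 1.5/4 = 0.375.

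In these examples the association arises because serostatus affects later uptake. If infection raised uptake, the ratio would exceed 1. The documents fix neither size nor direction.

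**Step 5: incident models.** Under the same sentence the 6-to-12-month items also enter the incident models. They would follow the 3-month outcome there, and a complete-case fit would again lose the control mine.

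**The case against.** The strongest defence is a different reading of the sentence. Section 7.4 makes test and vaccine uptake outcomes of hypothesis 4B, and section 1 says that 4B involves a separate but related study. Adding outcome variables could therefore mean fitting further models with uptake as the outcome. The reading is plausible, but it does not rescue the sentence. Mine type still cannot be a covariate for NM-only data, and face-covering and dust recorded after enrolment still enter the baseline model.

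Other objections stand and limit the point:

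- A reader might infer that all Table 7 variables follow the outcome. Two are baseline items and belong in the model, and only two are confined to one mine.
- A reader might infer that the coefficients would demonstrate reverse causation. The documents support only that some could reflect it. Dust is set by job assignment, and nothing says that infection alters the job. The late questionnaire asks for testing and vaccination history, which can include events before enrolment. Section 25 lets some miners first consent at or after six months, so for them the gap may be short.
- A reader might cite section 7.1 ("Conversely, we expect lower acceptance rates among those with prior infection (or vaccination") as the plan's own statement that infection changes these behaviours. That text concerns acceptance of the Aim 1 screening test. It says nothing about masking, dust, barriers or vaccine uptake.
- Hypothesis 4A concerns incident infection. The baseline model is exploratory and no primary result depends on it.
- The losses in step 2 assume the items enter as predictors in a complete-case fit. Section 13.4 names no method for missing data.

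**Conclusion.** The point holds, at minor to moderate severity. Followed literally, section 13.4 uses four variables recorded after enrolment to explain serostatus at enrolment. Two of them, in a complete-case fit, remove up to 58% of miners and leave the mine-type coefficient inestimable. The timing and coverage findings rest on the plan's own tables. The 58% also rests on enrolment at the section 5 ceilings, and the 41% of positives on the plan's assumed baseline rates. The possible bias from reverse causation is real but of unknown size and direction, and more plausible for masking and uptake than for dust. The documents do not support calling it a defect of the primary analysis, because the baseline model is exploratory. The same sentence does reach the incident models that test hypothesis 4A, and this is why it deserves more than an editorial note.

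**What to change.** Replace the closing sentence of the section 13.4 statistical analysis with text to this effect:

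- The baseline-seropositivity model will include mine type and only variables fixed or measured at enrolment: race/ethnicity, lung disease as recorded in the baseline survey, and other baseline-survey items.
- Face-covering use and dust intensity will enter only the incident-seropositivity models, with mine type. The text should also say how they are timed at the control mine, because Table 7 ties them to a screening test that is not done there.
- Barriers and facilitators will be analysed as predictors of test and vaccine uptake in a separate NM-only model for hypothesis 4B, without mine type.
- The vaccination-status covariate carried over from Aim 3 stays in the incident models.

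The third item is needed because section 13.4 is the only analysis text that covers these variables. Simply removing them from both models would leave hypothesis 4B with no stated analysis. The cost is a few sentences, fewer predictors in the baseline model and one more NM-only model to specify. No additional data or participants are needed.
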